5.6 Key exclusion criteria

- 1) Delivered prior to 32 weeks gestation in the EMR
- 2) Documentation of fetal demise or neonatal demise in the EMR
- 3) Currently pregnant or planning to get pregnant within the next 5 months
- 4) Does not speak English
- 5) Answers yes to any of the following questions:
 - Are you currently participating in any other weight loss or physical activity studies?
 - Do you have any medical conditions or other reasons why you could not participate in a 16-week weight loss or physical activity program?
- 6) Participants will be excluded after completing the run-in period if they do not complete the daily food log or their baseline BMI is $< 27 \text{ kg/m}^2$

6. Subject recruitment

We will use EPIC to identify a cross-sectional cohort of potentially eligible patients. Given the lag time between identifying potentially eligible patients and enrollment, we will identify women with a delivery occurring between the time of the data pull and 365 days prior. We will identify women based on the inclusion and exclusion criteria above. In order to optimally recruit women with a $\text{BMI} \geq 27 \text{ kg/m}^2$ at time of enrollment, we will use the following BMI criteria as documented in EMR:

- a. Pregravid $\text{BMI} \geq 30$, regardless of delivery BMI
- b. Pregravid $\text{BMI} 28-29.9$ and delivery $\text{BMI} \geq 33$
- c. If pregravid BMI missing, will include delivery $\text{BMI} \geq 33$

Potentially eligible patients will have their current address, phone number, email address, demographics, and clinical history abstracted. We will compare two approaches to patient recruitment (see study schema above, enrollment strategies)

- a. Email: For patients meeting inclusion criteria with a documented email address, we will randomize them to one of two recruitment emails that test behavioral approaches to engaging patients. Group 1 (reserved a spot) will receive an email notifying them that we reserved a spot for them in the upcoming online information session for a weight loss program designed for postpartum women. Group 2 (commit today) will receive an email asking participants if they are ready to commit to their health. Participants will be able to click on an embedded link in the email which will take them to a secure Redcap survey that will allow them to sign up for the virtual information session. Once participants sign up, they will receive a text reminder prior to the information session with the Zoom link. See

Appendix 2 for text of recruitment emails. For participants who do not respond, a reminder email will be sent 48 hours after the initial email.

- b. Mailer: We will combine participants who received an email but did not respond and patients who do not have an email address documented in the EMR. We will then randomize them to one of two mailer strategies: study mailer alone versus mailer plus gift. The mailer alone group will receive a flyer and mailer that focuses on achieving a healthy lifestyle postpartum and explaining the weight loss study (see Appendices 3 and 4). The mailer plus gift group will receive a mailed package containing the flyer and mailer plus a baby bib inscribed with study logo. Recruitment materials will be sent in waves until the expected number of participants are enrolled.

Patients will be able to sign up for the virtual information session hosted on Zoom through the study website (Redcap). Information on how to sign-up will be included on the mailer. In addition, patients will be able to call or text the study phone number to talk to a clinical research coordinator (CRC) in the Maternal and Child Health Research Center (MCHRC) to learn more about the study and/or sign up for an information session. We will try to accommodate patients who cannot make any of the scheduled sessions by scheduling additional sessions. In order to sign up, participants will need to provide their name, contact information, and date of birth.

As of 9/25/2021, we have reached target randomization using email recruitment alone. In order to compare the mailer versus mailer plus baby gift as outlined in Aim 2, we will continue recruitment using the mail strategy (see Study Schema, enrollment strategies above). When participants click on the Redcap link to sign up for a virtual information session, they will be informed that study enrollment is full. They will have the option to watch a 10-15 minute recorded video of study staff reviewing evidence based approaches to weight loss, which will be posted on the Recap website.

7. Subject compensation

All eligible participants will receive a scale if they complete the 1-week behavioral run-in period. Participants will receive \$30 after completing the 16-week intervention, virtual weigh-in and exit survey at the end of the study. Compensation will be delivered via Greenphire ClinCard.

8. Study procedures

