8.1 Consent

Interested participants will sign up for and attend an online information session that will be conducted by research staff over Zoom. Prior to the information session, participants will be emailed a copy of the informed consent form. In order to achieve a goal of 10 participants per session, we will invite 15-20 individuals for each session. The research staff will present a PowerPoint via screen share that reviews study rationale, expectations, adherence to the run-in period and interventions, and assessments. Participants will be muted for the presentation. Participants can choose to have their video turned on or off for the presentation, however they will be asked to have their first name displayed on their Zoom window.

At the end of the presentation, the participants will be un-muted. Participants who are interested in enrolling and providing informed consent will be asked to stay on the Zoom call and make sure their video is turned on. Participants who are not interested in enrolling will be invited to leave the call. At this point, research staff will review the informed consent form and allow participants to ask questions. Once all questions are answered, participants who are interested in providing informed consent will be asked to type their name in the chat box and indicate that they consent to participate. This will count as verbal consent provided in a group format. Documentation of verbal informed consent will be kept in the research record. Participants will be provided with details regarding how to contact the research team via phone at any time if they subsequently wish to withdraw from the study. Participants will be asked to electronically sign the consent form via Redcap when they receive the surveys as part of the behavioral run-in period and prior to randomization.

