d) Virtual weigh-in: All participants will be asked to complete a virtual weigh-in on the Monday following the kick-off session. Their weight on the Monday morning will serve as their baseline weight for the program. Participants in both arms will be asked to take a photo of the scale with the morning weight and send it to study staff by text or email. The number stays on the scale for 3 seconds after stepping off.

e) Health coach: A study staff member will be trained as a weight loss coach by the PIs. If participants in the intervention arm are having trouble using the platform, reaching their weight loss goals, or have stopped logging into the platform, research staff will reach out to help triage and troubleshoot any barriers.

g) At the end of the 16-week intervention, all participants will be asked to complete their final virtual weigh in and send a photo of the scale to study staff by text or email. At the end of the study, participants will be asked to complete an exit survey. In addition, participants will be offered an opportunity to participate in an online group feedback session on Zoom. Participants will receive \$30 incentive for completing the final weigh-in and exit survey. Study staff will abstract clinically relevant data from the electronic medical record to collect data on demographics, clinical comorbidities, and health care utilization. The collection of these data will obviate the need to further burden participants by asking them additional questions during the survey periods.

9. Analysis plan

Primary outcomes include:

- Enrollment rate, comparing email recruitment strategies (reserved a spot versus commit to health) and comparing mail strategies (mailer versus mailer plus gift)
- Change in weight from baseline to 16-week follow-up
- Proportion of participants losing $\geq 5\%$ of weight

Secondary outcomes:

- Study completion rate between 2 arms
- In the intervention arm, engagement with online BWL platform, including number of total logins, number of weeks with ≥ 1 login, number of weeks that calories, physical activity minutes, and body weight were reported for at least 5 of the 7 days

Exploratory outcomes

- Differences in any of the primary or secondary outcomes according to race/household income

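### The mailer versus mailer-plus-gift comparison has enrollment rate as its listed primary outcome, but it runs after enrollment closed, so section 9 needs a mail response outcome instead

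*Combined protocol and SAP*

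**What the plan says.** Section 9 (Analysis plan) opens its list of primary outcomes with "Enrollment rate, comparing email recruitment strategies (reserved a spot versus commit to health) and comparing mail strategies (mailer versus mailer plus gift". One label serves both the email and the mail comparison. Section 9 gives no numerator, denominator or time window for it.

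Section 6 (Subject recruitment) describes the mail comparison. Women who did not answer the email, together with women who have no email address on record, are randomized to a mailer alone or a mailer with a baby bib. A dated paragraph at the end of that section then changes the setting: "As of 9/25/2021, we have reached target randomization using email recruitment alone". The mail phase goes on for one stated reason: "In order to compare the mailer versus mailer plus baby gift as outlined in Aim 2, we will continue recruitment using the mail strategy". A woman who follows the link is not offered a place: "When participants click on the Redcap link to sign up for a virtual information session, they will be informed that study enrollment is full". She may watch a recorded video instead.

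The steps that lead into the trial come later. The recruitment link is meant to "take them to a secure Redcap survey that will allow them to sign up for the virtual information session". Section 8.1 puts the decision to join at the end of that session: "Participants who are interested in enrolling and providing informed consent will be asked to stay on the Zoom call". Section 8.2 places verbal consent there too, followed by electronic consent and the run-in, with randomization at the kick-off session.

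**The concern.** A listed primary outcome and the procedure meant to produce it no longer fit together. The mail phase is kept open solely to compare the two mailers, yet the outcome named for it lies beyond a step that is closed to every mail responder who uses the link.

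If the label is applied as the protocol uses the word, the comparison returns no events in either group and Aim 2 gets no answer about the gift. If the team means response to the mailing, the comparison is informative but undefined. It could count a click, a completed form, a call or text, or a video view, over any period and any denominator, and that choice could be made after the responses are seen. The shared label adds a further ambiguity: either the email outcome also becomes sign-up, or one bullet covers two different endpoints.

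**Working it through.** **The plan's own figure.** No sample size, expected rate or power is stated in the visible text for the mail comparison. The only derived number near it is the eligible pool in section 5.4: 8,400 × 0.30 × 0.60 × (1 − 0.20) = 1,209.6, stated as about 1,200. It reproduces, but it is a yearly planning estimate, not a number mailed.

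**Order of steps (sections 6, 8.1, 8.2).**
1. Mailing received.
2. Sign-up for the information session by link, or a call or text to the study line.
3. Information session, with verbal consent at its end.
4. Electronic consent, surveys and food log in the run-in.
5. Kick-off session with randomization.

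After the dated paragraph, the link route stops at step 2. The call or text route remains in the text, but no open place is described for women who use it.

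**Which step is enrollment?** There is no formal definition, so usage has to serve.
- Section 6 tells a woman who is signing up that enrollment is full, so sign-up and enrollment are separate things.
- Section 8.1 puts enrolling beside consent, at the end of step 3.
- Section 11.3 describes an enrollment procedure that includes questions and review of the consent form.

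All three point to step 3 or later.

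**What each meaning yields in the mail groups**, with n₁ and n₂ women randomized to the two mailers:

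| Meaning | Mailer alone | Mailer plus gift | Usable? |
|---|---|---|---|
| Consent (step 3) | 0/n₁ | 0/n₂ | No |
| Randomization (step 5) | 0/n₁ | 0/n₂ | No |
| Response (step 2) | observed | observed | Yes, once defined |

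For the first two rows:
- Risk difference: 0/n₁ − 0/n₂ = 0.
- Pooled proportion: 0/(n₁ + n₂) = 0. The pooled variance is therefore 0 and the chi-square statistic is 0/0, undefined.
- Odds ratio: (0 × n₂)/(n₁ × 0) = 0/0, undefined.
- Fisher's exact test: with no events, only one table fits the margins, so p = 1.

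None of these depends on n₁ or n₂, so mailing more women would not help.

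**The case against.** The best reply is that the sponsor means sign-up response. The dated paragraph was written in the knowledge that the target had been met. It says that mailing continues for the comparison, and its next sentence describes an event that can still be counted, the click to sign up. Aim 2 names recruitment as well as enrollment. The study schema, to which section 6 refers for these strategies, is not shown and might label the endpoint or give numbers mailed. This reply largely stands as to intent. It does not supply a definition, because section 9 still carries the enrollment label and no visible text redefines it.

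Three stronger readings are tempting but unsupported.
- A reader might infer that the mail comparison is bound to fail. The documents show that only for enrollment as consent or randomization; response can still be observed, and the randomized mail groups remain valid.
- A reader might infer that the mailing rule, "Recruitment materials will be sent in waves until the expected number of participants are enrolled", bars the phase because the target was already met. The later paragraph expressly continues mailing for another purpose and so displaces that rule. What remains is that the visible text states no number to be mailed.
- A reader might infer that responses cannot be traced to a mailer group. Section 6 says "In order to sign up, participants will need to provide their name, contact information, and date of birth", and contact details are abstracted from the medical record, so matching is feasible. The open question is whether those fields are captured before the message that enrollment is full.

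**Conclusion.** The concern holds as a mismatch between a listed primary outcome and the amended recruitment procedure. On the protocol's own usage of the word, enrollment is zero in both mail groups by design and the comparison is uninformative. On the reading that the sponsor probably intends, the comparison works but lacks a stated numerator, denominator and window.

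The conclusion rests on two assumptions: that no place was opened to women who call or text after the target was reached, and that the schema, which is not visible here, does not already define the mail endpoint.

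Severity is moderate. Section 9 does call this outcome primary, and the mail phase exists only for it. But section 2 makes recruitment strategy a secondary objective, the trial is a pilot, the weight outcomes are untouched, and the remedy is small.

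**What to change.** In section 9, replace the mail part of the bullet with sign-up response:
- **Numerator:** women who make a Redcap sign-up attempt, or call or text the study line, within a window fixed before analysis.
- **Denominator:** all women randomized to that mailer group.
- **Test:** Pearson chi-square or Fisher's exact. Section 9 already names both, though only for comparing sample characteristics.

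Capture the identifying sign-up fields before the message that enrollment is full, and log calls and texts in the same way, so that each response can be linked to its mailer group. State the number of women to be mailed. Limit the mail conclusion to recruitment response. State whether the email outcome uses this same definition or a separate enrollment definition; either can work if it is written down.

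The cost is a change of wording in the protocol and analysis plan plus modest response tracking. The price in interpretation is a narrower claim: the mail comparison would show which mailing draws more responses, not which one enrolls more women.

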8.1 Consent

Interested participants will sign up for and attend an online information session that will be conducted by research staff over Zoom. Prior to the information session, participants will be emailed a copy of the informed consent form. In order to achieve a goal of 10 participants per session, we will invite 15-20 individuals for each session. The research staff will present a PowerPoint via screen share that reviews study rationale, expectations, adherence to the run-in period and interventions, and assessments. Participants will be muted for the presentation. Participants can choose to have their video turned on or off for the presentation, however they will be asked to have their first name displayed on their Zoom window.

At the end of the presentation, the participants will be un-muted. Participants who are interested in enrolling and providing informed consent will be asked to stay on the Zoom call and make sure their video is turned on. Participants who are not interested in enrolling will be invited to leave the call. At this point, research staff will review the informed consent form and allow participants to ask questions. Once all questions are answered, participants who are interested in providing informed consent will be asked to type their name in the chat box and indicate that they consent to participate. This will count as verbal consent provided in a group format. Documentation of verbal informed consent will be kept in the research record. Participants will be provided with details regarding how to contact the research team via phone at any time if they subsequently wish to withdraw from the study. Participants will be asked to electronically sign the consent form via Redcap when they receive the surveys as part of the behavioral run-in period and prior to randomization.

8.2 Procedures

- a) Virtual information session: All potentially eligible and interested participants will first complete this session. At the end of the session, participants will provide verbal informed consent and will be invited to complete the behavioral run-in period.
- b) Behavioral run-in: participants will be emailed a link to a secure Redcap survey and asked to complete the following steps:
 - Electronic consent
 - Survey to determine eligibility
 - Profile with contact information, including correct address to send scale and contact preferences (email or text)
 - Online W9 form to facilitate delivery of incentives
 - Baseline demographic and study specific surveys (see Appendix 5)

Participants will be asked to complete 5 days of food logging. Participants can log food in MyFitnessPal (MFP), a free app for food tracking, and share with research staff or they can keep a food diary on paper and send in screenshots via text or email. Participants who provide informed consent and complete the run-in period will be sent a digital scale along with handouts in preparation for the virtual kick-off session.

- c) Virtual kick-off session: Once participants have received the scale, they will be eligible to sign up for a virtual kick-off session, during which participants will be randomized. Participants can sign up through the study website (via Redcap) or by contacting a CRC. This session will be conducted by research staff over Zoom. Randomization will occur at the beginning of the session and participants will be placed in one of two breakout rooms for the intervention or control arm.

- Control arm: study staff member will inform participants that they are in the control arm.

- Intervention arm: study staff will lead the Weight Loss 101 session. This session will review weight, calorie, and physical activity goals and evidence-based weight loss strategies, including food logging and daily weights. All participants will be asked to lose 10% of their body weight, corresponding to 1-2 lb/week over the 16-week study. Participants will receive a brief introduction to the online BWL study website. The session will also include information about weight loss and exercise while breastfeeding.

d) Virtual weigh-in: All participants will be asked to complete a virtual weigh-in on the Monday following the kick-off session. Their weight on the Monday morning will serve as their baseline weight for the program. Participants in both arms will be asked to take a photo of the scale with the morning weight and send it to study staff by text or email. The number stays on the scale for 3 seconds after stepping off.

e) Health coach: A study staff member will be trained as a weight loss coach by the PIs. If participants in the intervention arm are having trouble using the platform, reaching their weight loss goals, or have stopped logging into the platform, research staff will reach out to help triage and troubleshoot any barriers.

g) At the end of the 16-week intervention, all participants will be asked to complete their final virtual weigh in and send a photo of the scale to study staff by text or email. At the end of the study, participants will be asked to complete an exit survey. In addition, participants will be offered an opportunity to participate in an online group feedback session on Zoom. Participants will receive \$30 incentive for completing the final weigh-in and exit survey. Study staff will abstract clinically relevant data from the electronic medical record to collect data on demographics, clinical comorbidities, and health care utilization. The collection of these data will obviate the need to further burden participants by asking them additional questions during the survey periods.

9. Analysis plan

Primary outcomes include:

- Enrollment rate, comparing email recruitment strategies (reserved a spot versus commit to health) and comparing mail strategies (mailer versus mailer plus gift)
- Change in weight from baseline to 16-week follow-up
- Proportion of participants losing $\geq 5\%$ of weight

Secondary outcomes:

- Study completion rate between 2 arms
- In the intervention arm, engagement with online BWL platform, including number of total logins, number of weeks with ≥ 1 login, number of weeks that calories, physical activity minutes, and body weight were reported for at least 5 of the 7 days

Exploratory outcomes

- Differences in any of the primary or secondary outcomes according to race/household income

To compare sample characteristics between arms we will use t-tests or Wilcoxon rank-sum tests for continuous variables and Pearson chi square tests or Fisher's exact tests for categorical variables. Generalized linear mixed effects models will be used to assess for differences in weight, given repeated observations. We will use fixed effects to adjust for study arm, baseline weight, and calendar month, which may reflect seasonal variations that make weight loss harder or easier. We will conduct a number of sensitivity analyses to evaluate the robustness of our findings. All hypothesis tests will be two-sided using a two-sided alpha of 0.05 as our threshold for statistical significance. We will use Stata and/or SAS to analyze the data. We will use multiple imputation for missing data.

10. Investigators

[name], MPH is the co-Principal Investigator (PI) and is an Assistant Professor of Medicine at the Perelman School of Medicine. She is Director of the Women's Cardiovascular Health Program. She has experience running lifestyle interventions among postpartum women.

[name] is the co-Principal Investigator (PI) and is a Professor of Psychology in Psychiatry at the Perelman School of Medicine. She is Director of the Center for Weight and Eating Disorders. She has extensive experience designing and running behavioral weight loss clinical trials.

[name] is a co-investigator. She is Associate Professor in the Department of Allied Health Sciences and Co-Director of the Weight Management Research Group at the University of Connecticut (UConn). She developed the online BWL platform along with collaborators at the University of North Carolina.

The Clinical Research Coordinator has experience with administering studies involving interventions with pregnant and postpartum populations and also has experience training Research Assistants to follow study protocols.

11. Human research protection

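### The baseline for the weight outcomes is measured after randomization and the first intervention session; the bias is probably small and toward no difference, and it is cheap to limit or report

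*Combined protocol and SAP*

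**What the plan says.** The order of events is in Section 8.2 (Procedures). A woman who finishes the run-in is sent a digital scale. "Once participants have received the scale, they will be eligible to sign up for a virtual kick-off session", so the scale is in her home before she is assigned. At kick-off, "Randomization will occur at the beginning of the session and participants will be placed in one of two breakout rooms". In the control room a "study staff member will inform participants that they are in the control arm". In the other room staff lead Weight Loss 101: "This session will review weight, calorie, and physical activity goals and evidence-based weight loss strategies, including food logging and daily weights".

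The weigh-in comes on the Monday after kick-off, by photo of the home scale in both arms. "Their weight on the Monday morning will serve as their baseline weight for the program". Section 5.1 gives the same order, and it lists the Weight Loss 101 session among the contents of Arm 2.

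Section 9 makes change in weight from baseline and the proportion losing at least 5% primary outcomes. On the model it says: "We will use fixed effects to adjust for study arm, baseline weight, and calendar month". It does not name the reference weight for the 5% outcome.

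A baseline BMI is used for exclusion. Section 5.4 puts that exclusion during the run-in and Section 5.6 after its completion. Neither says which weight the BMI uses or when it was taken.

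On trial status, Section 6 states: "As of 9/25/2021, we have reached target randomization using email recruitment alone". Later sign-ups are told that enrollment is closed ("they will be informed that study enrollment is full").

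**The concern.** A baseline should be fixed before assignment can influence it. Here each woman knows her arm when she takes the reference weight, and the intervention arm has already had one of its components. If that session leads to any loss before Monday, the intervention arm starts from a lower reference and the loss is not counted. The continuous outcome shrinks toward no difference, and an intervention woman must lose slightly more than 5% of her pre-randomization weight to count as a responder.

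Using the Monday weight as a covariate does not help, because the covariate itself carries the early effect.

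Two further routes are possible in principle: different weighing conditions by arm, and a different share of women by arm who never send the Monday photo. The documents give no rate for either.

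**Working it through.** The plan gives no effect size, SD or power for the weight outcomes, so there is no figure of its own to reproduce. The check sizes the possible shift.

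**Inputs from the documents.** Goal rate 1-2 lb/week and 10% of body weight in 16 weeks (Sections 5.1 and 8.2); 16 weeks = 112 days; 40 and 20 women (Section 5.4).

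**Assumptions.** The gap *d* from kick-off to the following Monday is 1-7 days, since the weekday of kick-off is not stated. Intervention women lose at the full goal rate from kick-off and controls lose nothing, which makes the results upper figures. The baseline slope *b*, the SDs and the correlations below are not in the documents.

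**1. Shift in the baseline.** *s* = rate × *d*/7, with 1 lb = 0.4536 kg.
- *d* = 1: 0.4536/7 = 0.06 kg; 0.9072/7 = 0.13 kg.
- *d* = 7: 0.45 kg; 0.91 kg.

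At a constant rate the part left out is *d*/(112 + *d*) of the loss since kick-off: 1/113 = 0.9% to 7/119 = 5.9%.

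**2. After adjustment.** The adjusted arm effect is the difference in 16-week weight minus *b* times the difference in baseline weight. A baseline lower by *s* in the intervention arm therefore attenuates the effect by *b* × *s*. For *d* = 7:
- *b* = 0.9: 0.41-0.82 kg.
- *b* = 1.0: 0.45-0.91 kg.

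So 90-100% of the shift remains.

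**3. The 5% outcome, as a share of pre-randomization weight.**
- (a) Constant rate throughout: *L* = 0.05(112 + *d*)/(112 + 0.05*d*). *d* = 1: 5.65/112.05 = 5.04%. *d* = 7: 5.95/112.35 = 5.30%.
- (b) Days before Monday at the goal rate of 10% in 16 weeks: *g* = (0.10/16)(*d*/7), and the threshold is 1 − 0.95(1 − *g*). *d* = 1: *g* = 0.089%, threshold 5.08%. *d* = 7: *g* = 0.625%, threshold 5.59%.

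**4. Women whose responder status could change, 7-day gap.** If percent change is normal, the share is at most shift × 0.399/SD, with SD assumed at 4-8 points.
- (a) Shift 0.30: 3.0 points (SD 4) or 1.5 points (SD 8), which is 1.2 or 0.6 of 40 women.
- (b) Shift 0.59: 5.9 or 2.9 points, which is 2.4 or 1.2 of 40.

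**5. Could chart BMI stand in for women already randomized?** Section 6 uses pregravid or delivery BMI from the medical record to find women. Suppose 16-week weight were compared between arms with that BMI as covariate. With an assumed weight SD of 15-20 kg and correlation *r* of 0.7-0.9, SE = SD × √(1 − *r*²) × √(1/40 + 1/20).
- SD 15, *r* = 0.9: 15 × 0.436 × 0.274 = 1.8 kg.
- SD 20, *r* = 0.7: 20 × 0.714 × 0.274 = 3.9 kg.

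The 95% half-width is about 3.5-7.7 kg, against a bias of at most 0.91 kg. That analysis could neither show nor exclude the bias.

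**The case against.** The best defence is that Monday is the right start. Section 5.2 begins the 16 weeks after Weight Loss 101, Section 5.1 puts the weigh-ins at the two ends of the 16-week period, and lessons are posted on Mondays. A pre-kick-off reference would measure 16 weeks plus a gap that varies between women; in scenario (a) the rise from 5.00% to 5.30% is simply those extra days. This stands in part: the matter is partly a choice of interval. It does not remove the concern, because Section 5.1 makes Weight Loss 101 part of what is compared with usual care.

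The size is also an upper figure. Before Monday both arms have logged food and received the scale and handouts, and usual care also gets educational resources. Only one session separates the arms. This stands.

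Three stronger readings are tempting, and the documents do not support them.
- A reader might infer that the baseline can be biased in either direction, including in favor of the intervention. The weighing procedure is the same in both arms and documented by photo, and nothing shows different weighing conditions or missing baselines by arm. It is a possibility to report on, not a finding.
- A reader might infer that the baseline BMI is the Monday weight, so that women are excluded after randomization. Sections 5.4 and 5.6 tie the exclusion to the run-in, and Section 5.4 plans 85 consents to reach 60 randomized, so it falls before assignment. Only its source and date are missing.
- A reader might infer that a new weigh-in would repair this trial. The randomization target has been reached, so for most or all women only analysis and reporting can change.

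**Conclusion.** The point holds in a limited form. The only weight defined as baseline is taken after randomization, arm disclosure and one intervention session, and both the change outcome and the model rest on it. The probable effect is a small understatement of the intervention's benefit: at most 0.06-0.13 kg for a 1-day gap and 0.45-0.91 kg for a 7-day gap, of which 90-100% survives adjustment. At most about 0.6-2.4 of 40 intervention women would change responder status with a 7-day gap.

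These figures assume loss at the full goal rate in one arm and none in the other; the responder figures also rest on an assumed SD. Less is likely in practice. The order of events is certain from the text; the size is a bound, not an estimate. Nothing here invalidates the trial. It is a cheap improvement.

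**What to change.** 1. **Any woman still to be randomized.** Ask for a photo weight on the study scale after it arrives and before assignment at kick-off. Use it as the analysis baseline, the model covariate and the 5% reference. Keep the Monday weight as the program start weight.
2. **Women already randomized.** Keep all of them in the analysis. Report by arm the interval from kick-off to weigh-in and the number with no Monday weight. If a pre-randomization weight was recorded for the BMI check, repeat the weight analyses with it as the reference, as a sensitivity analysis, and note that it may not come from the study scale. Section 9 already promises sensitivity analyses without naming any. Do not use the chart BMI for this purpose; it is too imprecise.
3. **Wording.** State the source and date of the weight behind the baseline BMI so that Sections 5.4, 5.6 and 8.2 agree, and name the reference weight for the 5% outcome.

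**Cost.** For women already randomized: a few lines of analysis plan, one table by arm and, if the data exist, one extra analysis. For later women: one extra photo with a scale already in hand, a possible delay to kick-off for a woman who has not sent it, and a follow-up interval slightly longer than 16 weeks that varies between women.
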